Medical record abstraction (MRA); Post disclosure: 10 days (T1); 3 months (T2); 9 months (T3); Medications (Meds); Genetic counseling (GC); Physician (MD)

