Psychosocial impact of genetic testing and patient uncertainty will be assessed using both the adapted PAGIS Certainty Scale and the FACToR.²³ The FACToR is a 12-item measure developed by CSER1 colleagues at the University of Washington that applies across disease contexts and also includes items related to uncertainty, test-related distress, and positive experiences. Uncertainty about genetic testing results will be assessed using the PAGIS. A 5-item measure by Read and colleagues (Psychological Adaptation to Genetic Information Scale; PAGIS certainty subscale).⁸

Tool usability/usefulness/acceptability will be assessed for patients who view the HOPE-Genomics tool (Arms 2 and 3) approximately 10 days and 3 months after results disclosure. HOPE-Genomics usability/acceptability will be assessed using two instruments. To assess system usability, we will use the System Usability Scale (SUS).⁹ The SUS is a 10-item measure that evaluates a variety of aspects of system usability including the perceived complexity of a system and the need for support and training to facilitate use. We will also use an adapted version of the Electronic Self-Report Assessment-Cancer (ESRA-C).¹³ The ESRA-C is a 6-item measure that assesses participants' opinions about a web-intervention (e.g., easy and enjoyable, acceptability of time required to navigate, overall satisfaction). The ESRA-C is written at a 5th-grade reading level and is highly reliable (Cronbach alpha 0.76).

Motivations for sharing genetic test results will be assessed using a modified 9-item measure adapted from our CSERII study and the Development of the Informing Relatives Inventory (IRI) by de Gues and colleagues.¹⁰ Patients will be asked to rank the importance of various reasons for sharing genetic test results on a 5-point scale, from "Not At All Important" to "Very Important." This measure will only be included in the 3-month follow-up survey and will be included as an exploratory measure.

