We will test if the use of HOPE-Genomics will result in higher rates of uptake of evidence-based genetically guided care (e.g., patient receipt of guideline concordant care, cascade testing) than usual care: Our primary goal will be to assess whether or not the uptake of contextual guideline-concordant care differs between the two arms. The primary objective is to test the null hypothesis of no intervention effect on the outcome. We expect that patients in the intervention arm will have higher rate of uptake of contextual guideline-guided care than patients in the control arm. A two-sided Type I error of 0.05 will be used for all statistical tests. We will consider two-sided p-value less than 0.05 as a statistically significant. Patients will be considered concordant ($Y=1$) if they undergo a predetermined percentage of genetically guided care and discordant ($Y=0$) otherwise. Using an intention-to-treat analysis, the proportion of concordant patients will be modeled using the logistic regression approach for binary outcome (PROC LOGISTIC in SAS [Cary, N.C.]). We will use compound symmetry and unstructured working correlation matrix to account for correlation between patients within the same physician. The odds ratio of the concordant patients between the intervention and control arms will be calculated using the group coefficient in the Logistic model. The significance of the coefficient will be tested to determine treatment group difference. In addition, we will use Kauermann and Carroll (KC) correction for robust SEs if the number of physicians is small.¹¹ To evaluate the success of randomization, we will test the differences in characteristics of physicians and patients between the two arms. The Logistic model will include statistically significant characteristics as covariates. Logistic will also be used to model the percentage of the rate of uptake of the genetically guided care per patient, treated as a binomial variable, and include the within-physician correlation, to test for treatment group difference.

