Test-related distress: We hypothesize that patients who view HOPE-Genomics will have lower test-related distress than patients in the usual care group: Patients will be assessed at 3 post-disclosure time points (T1-T3) using the PAGIS Certainty Scale and the FACToR. Some patients may have little test-related distress, whereas others may score higher (e.g., if testing reveals cancer or non-cancer related disease risk). Test-related distress is thought to decrease with time from the disclosure visit. We will summarize test-related distress at each time point, as well as change score. We will examine baseline characteristics to evaluate the potential for bias. In addition to complete case analysis, sensitivity analyses (e.g., using weighted methods) may occur to evaluate bias. We will use clustered Wilcoxon test for mean score comparison between groups at each time point. In addition, mean change in score from T1 to T3 will be modeled using GEE model adjusting for patient characteristics. We will use Autoregressive (AR1) and compound symmetry working correlation matrix to account for repeated measurement correlation and within-physician correlation. The significance of the coefficient will be tested to determine difference between two groups.

General genomic knowledge: We hypothesize that patients in the Return of Results plus Pre-test Education (Arm 3) arm will have better general genomic knowledge than the Return of Results only and Usual Care arms (Arms 1/2). To examine this, we will compare the pre/post test scores between the intervention group (Arm 3) and the control groups (Arms 1/2). The pre/post test scores will be calculated by taking the difference in score between pre/post tests and then comparing the mean differences with an independent T-test between control groups (Arms 1/2) versus the exclusive exposure to the HOPE-Genomics tool educational content (Arm 3). We also hypothesize that Arm 3 will have better knowledge of the difference between germline and somatic testing, as measured in the modified Lung-MAP instrument, which has been adapted and implemented in our survey. We will test this difference as above, testing the mean difference in scores of the modified Lung-MAP instrument across Arms 1 and 2 vs Arm 3.

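### The knowledge t-test on raw differences is less precise than ANCOVA on the baseline score and leaves its post survey unnamed; the distress GEE needs one clarifying line

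*Combined protocol and SAP*

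**What the plan says.** **Knowledge.** Section 6.2.3 expects Arm 3 to have better general genomic knowledge than Arms 1 and 2. It takes each patient's difference between a pre and a post test and compares the mean differences with an independent t-test. The modified Lung-MAP score, on germline versus somatic testing, is to be handled the same way. Neither survey is named. Table 1 marks genomic knowledge at four surveys: baseline, pre-education, T1 and T2.

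Section 6.1 describes pre-testing at baseline, then disclosure, then post-testing. Section 4.3 has all arms complete the pre-test education survey 2-3 days after baseline and before disclosure. By then Arm 3 has viewed the tool and the other arms have seen only the pamphlet. Arm 2 gets the educational content once its results are in the tool.

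**Distress.** The hypothesis in Section 6.2.3 is about level: "We hypothesize that patients who view HOPE-Genomics will have lower test-related distress than patients in the usual care group". Level is compared directly: "We will use clustered Wilcoxon test for mean score comparison between groups at each time point". The covariate-adjusted model follows: "In addition, mean change in score from T1 to T3 will be modeled using GEE model adjusting for patient characteristics". AR(1) and compound-symmetry working correlations are then specified for repeated measurements and for patients of the same physician, and the paragraph ends: "The significance of the coefficient will be tested to determine difference between two groups". In Section 6.2.2, by contrast, the coefficient is identified: the odds ratio "will be calculated using the group coefficient in the Logistic model". The two distress instruments are PAGIS certainty and FACToR; according to Section 4.1.2 the latter "also includes items related to uncertainty, test-related distress, and positive experiences".

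**The concern.** A raw difference fixes the weight on the baseline score at 1, whatever its correlation with the post score. ANCOVA estimates that weight, so precision is lost for no return when the baseline score is already in the database.

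The choice of post survey matters more when the baseline-to-post correlation is high, because ANCOVA then gains little. The Section 6.2.3 comparison treats Arm 3 as the only arm exposed to the educational content. That is true only before disclosure. Afterwards Arm 2, half of the comparison group, can view the same content. If post means T1 or T2, the contrast is diluted and answers a different question from the one stated. An unnamed survey also leaves the choice open until data are in hand.

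For distress, the adjusted model is worded on change between two post-disclosure visits while the hypothesis is about level, and the tested coefficient is not identified. It is also not said which direction is favourable on each scale: a certainty score and positive-experience items need not run the same way as distress.

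**Working it through.** **The plan's own figure.** The only power statement is for primary recall (Section 6.2.1): 39% against 54%, 130 against 260 patients, two-sided 0.05, 80% power. It reproduces at 80.2%. No power is given for the Section 6.2.3 outcomes.

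**Inputs.** 390 analysed patients, 130 per arm (Sections 6.1 and 6.2.1), so Arm 3 has 130 and Arms 1 and 2 together have 260. The effect size and the baseline-to-post correlation r are not in the documents. I assume 0.25 SD and r from 0.3 to 0.8, with equal SDs at the two surveys.

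**Precision.** In units of the score variance, a raw difference has variance 2(1-r) and ANCOVA has 1-r². The ratio is (1-r²)/(2(1-r)) = (1+r)/2. The group-size factor is sqrt(1/130 + 1/260) = 0.1074. Power is Φ(0.25/SE - 1.96), with SE = 0.1074 × SD.

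| r | Variance, difference | Variance, ANCOVA | Ratio | Power, difference | Power, ANCOVA |
|---|---|---|---|---|---|
| 0.3 | 1.40 | 0.91 | 0.65 | 50% | 68% |
| 0.5 | 1.00 | 0.75 | 0.75 | 64% | 77% |
| 0.7 | 0.60 | 0.51 | 0.85 | 85% | 90% |
| 0.8 | 0.40 | 0.36 | 0.90 | 96% | 97% |

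For example, at r = 0.5 the difference gives 0.25/0.1074 = 2.33, and Φ(0.37) = 64%. ANCOVA gives 0.25/(0.1074 × 0.866) = 2.69, and Φ(0.73) = 77%. A variance 10-35% lower is worth 0.10 × 390 = 39 to 0.35 × 390 = 137 patients.

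**Which survey is post.** Let v be the share of Arm 2 that has viewed the content. Assume those patients gain as much as Arm 3 and that Arm 3 keeps its gain. Arm 2 is half of the comparison group, so the contrast is 0.25 × (1 - 0.5v). ANCOVA power at r = 0.5 is then:

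- v = 0 (pre-test education survey): 0.25 SD, 77%
- v = 0.5: 0.1875 SD, 52%
- v = 1: 0.125 SD, 27%

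A value of v below 1 at T1 is plausible. Section 4.4 puts results in the tool about 3-14 days after they reach the EHR, and Section 4.5.1 sends the T1 survey about 10 days after the same event.

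The text points two ways. Section 6.1 places post-testing after disclosure. Section 4.3, and the Section 6.2.3 description of Arm 3 as the only exposed arm, fit only the survey before disclosure.

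**Distress.** Let the benefit be b1 at T1 and b3 at T3. A contrast of T1-to-T3 change estimates b1 - b3, which is zero if the benefit is constant. A group effect on the repeated score estimates level. One change score per patient would leave no repeated measurements to correlate, so the AR(1) sentence fits the repeated-score model better. What is missing is a statement of the response and the coefficient.

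**The case against.** The t-test on differences is valid under randomisation, so ANCOVA corrects no bias. Baseline and the pre-test education survey are only 2-3 days apart, so r may well be high, and at 0.8 the gain is one percentage point of power. Both points stand. They limit the size of the improvement, but it costs nothing.

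Three stronger readings are tempting, and the documents do not support them.

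- *The distress hypothesis is tested only through change, so a lasting benefit would be missed or a fading one would count against the tool.* Read literally, with an assumed 0.3 SD benefit gone by T3 and r of 0.3-0.7, usual care would show a significantly larger fall in 66-95% of trials. But level is already compared at each visit by the clustered Wilcoxon test, the GEE is an addition to it, and the AR(1) sentence favours the repeated-score model, in which the problem disappears. Change over time is also a reasonable second question, since the plan expects distress to fall.
- *The survey called pre-test could serve as the pre score, putting Arm 3's gain into its starting value and reversing the sign.* Section 6.1 ties pre-testing to baseline.
- *Arm 3 may see the tool before its baseline survey, because Section 4.3 gives access straight after enrolment.* Section 4.1.1 has the baseline survey completed at consent, and the Appendix G invitation to view the tool thanks the patient for completing the first survey. That largely answers the point.

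**Conclusion.** The knowledge point holds as a gain in precision and a gap in specification. The planned test is not invalid. ANCOVA lowers the variance by 10-35% for r of 0.8 to 0.3; at 0.25 SD that is worth between 1 and 18 points of power. Naming the post survey matters because the contrast could halve, from 0.25 to 0.125 SD, if all of Arm 2 has viewed the content and gained equally. Effect size, correlation and viewing share are all assumed; the variance ratio depends only on r and on equal SDs at the two surveys.

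For distress, only a clarification is warranted. A reader might infer that the level hypothesis goes untested, but Section 6.2.3 itself tests it. All of these outcomes are exploratory, and the primary recall comparison and the sample size are unaffected.

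**What to change.** 1. For general knowledge and the modified Lung-MAP score, replace the t-test with ANCOVA: post score on arm (Arm 3 against Arms 1 and 2), with the baseline-survey score as covariate.
2. Name the pre-test education survey as post for every scale it contains, and reconcile Section 6.1 with this. That is a decision about the comparison as well as a matter of wording, because Section 6.1 now places post-testing after disclosure. Report T1 and T2 as retention, with Arm 3 against Arm 1 shown beside the pooled contrast. If a scale is not in the pre-test education survey, name the later survey used and show the same two contrasts.
3. For distress, state that the GEE response is the repeated T1-T3 score and that the tested coefficient is the randomised-group effect on level (Arms 2 and 3 against Arm 1). Report T1-to-T3 change as a separate question. Give the favourable direction for PAGIS certainty and for FACToR.

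The cost is a few sentences in Section 6.2.3 and one reconciliation with Section 6.1. Data, visits and software stay the same.

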7.0 MONITORING AND PERSONNEL RESPONSIBLE FOR MONITORING

The Principal Investigator, collaborators, and study staff will work closely to ensure adequate monitoring of the study. The Principal Investigator is responsible for monitoring protocol conduct and reporting to the COH DSMB any adverse events related to study procedures.

8.0 HUMAN SUBJECT ISSUES

We will take measures to protect patients, including the exclusion of patients who are too ill to participate in the study. [name], the Co-Investigators and the Collaborating Investigators are experienced working with patients with cancer and have undergone training designed to ensure the adequate protection of human subjects.

8.1 Potential Risks to Participation

This study involves the completion of study-related surveys and the viewing of a computer-based educational tool. No invasive procedures are involved and hence the physical, psychological and social risks to participants are minimized. The risks and discomforts of this study are minimal and may be associated with answering potentially sensitive questions on surveys. Data will be retrieved from existing medical records and laboratory results as per the research protocol needs for identifying patient outcomes and populating the educational intervention. Patient confidentiality will be strictly maintained and a breach in confidentiality is not anticipated and will be mitigated by following procedures detailed in Section 5, “Data and Safety Monitoring, Unanticipated Problems, and Protocol Compliance.” In creating a patient-facing application that discloses genetic test results, this study involves the transfer and storage of PHI (patient name, date of birth, medical record number, biological sex, cancer type, ordering provider, and genetic test results) from a password-protected database in REDCap to the HOPE-Genomics platform. As mentioned in Section 4.2, each participant is assigned a unique FHIR ID that cannot be linked or traced back to any patient PHI. Only team members with appropriate administrative rights have access to participants’ FHIR IDs and corresponding MRNs. Further, no PHI is shared between the HOPE-Genomics platform and Google Analytics, which is purely used for collecting basic user engagement metrics (i.e., number of page clicks, time spent on a page in the tool).

Our informatics team performs cybersecurity scans every week on the entire HOPE-Genomics application to look for any vulnerabilities. Any detected vulnerabilities are assessed and fixed as needed.

8.2 Potential Benefits to Participation

The patients may not directly benefit from study participation. However, the data gained through this study stands to potentially improve their genomic knowledge and quality of patient-centered care. In addition, it may improve education and care quality for future patients.

8.3 Potential Benefits to Others

Information from this study is expected to contribute to the understanding of how to optimally return genomics results to cancer patients and to better communicate important genomics concepts to patients. This information may be especially important as rates of genomic testing increase without proportional increases in clinicians to return these results.

8.4 Alternatives to Participation

Patients can choose not to participate, and this will not impact their medical care at City of Hope in any way.

8.5 Informed Consent

The PI or IRB-approved named designate will explain the nature, duration, purpose of the study, potential risks, alternatives and potential benefits, and all other information contained in the informed consent document. In addition, they will review the experimental subject's bill of rights and the HIPAA research authorization form. Research subjects will be informed that they may withdraw from the study at any time and for any reason without prejudice, including as applicable, their current or future care or employment at COH or any other relationship they have with COH. Research subjects will be afforded sufficient time to consider whether or not to participate in the research.

8.6 Registration into Clinical Trials On-Line system

All participants of this study will be registered into OnCore at COH for this trial.

8.7 Participant Withdrawal from Research

At any time after signing the informed consent document, participants may elect to withdraw from participation in this protocol as follows: A participant may (1) withdraw from future study activities but permit clinical data collection to continue, (2) withdraw from future study activities and disallow the collection of clinical data, (3) remain amenable to study activities but disallow retention of PHI data, or (4) elect to withdraw completely from the study whereby all data will no longer be made available for research. Participant withdrawal, including the nature of withdrawal, will be documented in the Master List which will be kept in a password-protected file, accessible only by authorized study staff using secure COH computers. The request to withdraw from studies will also be documented in the patient's medical record via Epic. If they do not wish to participate but are interested in exploring other options such as talking with their care team or a social worker, we will provide appropriate referrals.

8.8 Financial Obligations and Compensation

In the event of physical injury to a research participant resulting from research procedures, appropriate medical treatment will be available at the COH to the injured research participant, however, there are no plans to provide financial compensation. Such an event is extremely unlikely given the nature of the study activities.

The research participant will receive \$25 for taking part in this study. For patients who choose to have an on-site study visit, we will also cover the cost of valet parking.

8.9 Confidentiality

The records related to subject identity will be kept in separate research files and will be accessible only to Principal Investigator and authorized study staff. Any information allowing identification of the subjects will not be included in any published report or any computerized records. Data will be presented as aggregate or group data. The principal investigator and study staff will be the only ones having access to the collected data. The results will not be available to insurance carriers or employers.

The confidentiality of each participant will be rigorously maintained using existing City of Hope standards. HIPAA and state/federal government regulations for protecting patient privacy and security will be strictly observed. Researchers and staff who are not authorized to see PHI will be blocked from viewing PHI following HIPAA guidelines using role-based access controls. For example, unauthorized web app developers will not be allowed to view PHI.

No patient or subject identifiable information will be given to third parties, including family members, unless that subject has given written or witnessed consent to do so. The results of research studies may be published but subjects will not be identified in any publication.

9.0 DEVIATIONS

A deviation is a divergence from a specific element of a protocol and that occurred without prior IRB approval. Deviations from the approved protocol should be avoided, except when necessary to eliminate an immediate hazard to a research participant. A Corrective and Preventative Action (CAPA) plan should be developed by the study staff and implemented promptly to avoid similar issues in the future. All deviations from the protocol must be documented in study source documents and promptly reported to the DSMC and IRB.

9.1 Reporting Deviations

Investigators may deviate from the protocol to eliminate immediate hazards for the protection, safety, and well-being of the study subjects without prior IRB approval. For any such deviation, the PI will notify the DSMC and IRB, within 5 calendar days of its occurrence by electronic submission of a Deviation Notice via iRIS.

9.2 Single Subject Exception (SSE) Amendment Request

Deviations from the written protocol that are not done to eliminate an immediate hazard(s) for the protection, safety and well-being of study subjects but may increase risk and/or alter the protocol integrity require prior IRB approval. The deviation is submitted as a Single Subject Exception (SSE) amendment request. An IRB approved SSE does not need to be submitted as a protocol deviation to the DSMC. The SSE should be submitted according to the IRB guidelines and COH Institutional Deviation Policy and submitted via iRIS. A deviation that is not an SSE (i.e., discovered

after the occurrence) must be reported to the COH DSMC and IRB according to the COH Institutional Deviation Policy and submitted via iRIS.

The main risk to participants is the potential loss of confidentiality. Participants will be assigned a unique study identification number that will be stored separately from personal identifiers. Study materials will be marked with these numbers but no other identifying information. All data will be stored on password-protected computers. Access to data containing personal identifiers will be secured with a password filing system and will be restricted to authorized study staff. All study cabinets and computer databases will be secured in offices that are locked when not in use. No data regarding individuals' responses will be provided to any third party or to study participants. Any paper records will be kept in locked file cabinets for 1 year after paper publication and then destroyed.

Another risk of this study is that participants may feel upset when answering study-related questions. If they feel upset during the surveys, they can stop participating at any time or choose not to answer any question for any reason. As noted in section 7.0, if the participant feels upset and would like referral for psychological counseling, the principal investigator will provide them with a referral to a mental health professional/social worker at City of Hope as appropriate.

